3.6.4.5.4 Sheehan Suicidality Tracking Scale

Suicidality will be monitored during the trial using the Sheehan-STS.²¹ The Sheehan-STS is a prospective scale that assesses treatment-emergent suicidal thoughts and behaviors. Each item of the Sheehan-STS is scored on a 5-point Likert scale (0 = not at all; 1 = a little; 2 = moderate; 3 = very; and 4 = extremely). The Sheehan-STS can be analyzed as individual item scores, suicidal ideation subscale score, suicidal behavior subscale score, or total score. The “Screening” Sheehan-STS form was completed at the screening visit of the double-blind Trial 331-14-213 to determine eligibility. The “Since Last Visit” Sheehan-STS form will be completed baseline and Week 12/ET during Trial 331-201-00182. The medical monitor should be contacted if a score of 3 or 4 on any one question 3 through 6 or 11 or a score of 2 or higher on any one questions 1a, 7 through 10, or 12, or 18, or if suicide results in death.

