3.6.4.5.5 Mini-Mental State Examination

The Mini-Mental State Examination (MMSE)²² is a brief practical test for assessing cognitive dysfunction. The test consists of 5 sections (orientation, registration, attention

Protocol 331-201-00182

and calculation, recall, and language) and has a total possible score of 30. The MMSE is completed at baseline and Week 12 or ET.

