9.6 Mini-Mental State Examination

The mean changes from baseline in MMSE for trial visits during the open-label treatment phase will be summarized by descriptive statistics. Descriptive statistics will be summarized at each visit using the OC data set and at the last visit (Week 12/ET) using the LOCF data set.

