10.1 Study Visit Windows

Trial visit windows will be used to map visits using trial day intervals. This visit window convention applies to tables and listings for all efficacy and safety scales (CMAI, CGI-S, SAS, AIMS, BARS, MMSE and Sheehan-STS). This derived trial window variable will be named as WEEK and will be footnoted. In listings it will be listed along with the case report form (CRF) trial visit.

Table 10.1-1 below shows classifications for trial day intervals in the open-label treatment period. The variable “target day” is defined using the number of days since the start of open-label brexpiprazole dosing. The first day of open-label brexpiprazole dosing is defined as “Day 1”. If more than one observation falls within a particular trial day interval, then the last observation within that interval is used. Evaluations occurring more than 7 days after the last

SAP 331-201-00182

open-label brexpiprazole dosing date will not be mapped into study visit windows and will be excluded from the analysis.

Table 10.1-1 Mapping of the Analysis Visit for the Open-label Treatment Period		
Analysis Visit	Target Study Day ^a per Protocol	Study Day Interval^a (endpoint inclusive)
Day 1	1	1
Week 1	7	2 to 10
Week 2	14	11 to 28
Week 6	42	29 to 63
Week 12	84	64 to 91

^a Relative to the first day of IMP in the open-label treatment period.

^b Evaluations occurring more than seven days after the last dosing date of IMP in the open-label treatment period will be excluded from the efficacy analyses.

The preceding algorithm ensures that all observations collected at an ET visit or any other unscheduled visit will be mapped to an analysis visit. In instances where multiple observations (of same parameter on the same subject) fall into one study day interval, all values of the multiple observations in the study interval will be included for listings, but only the last observation will be used for the by-visit analysis or summary.

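### SAP 10.1 maps early-termination and unscheduled scale scores into visits where the scale is not scheduled, and at Week 6 lets a later exit score replace the scheduled SAS, AIMS or BARS score

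*SAP*

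**What the plan says.** **Windowing.** SAP 10.1 states its scope: "This visit window convention applies to tables and listings for all efficacy and safety scales (CMAI, CGI-S, SAS, AIMS, BARS, MMSE and Sheehan-STS"). Table 10.1-1 assigns Days 2–10 to Week 1, 11–28 to Week 2, 29–63 to Week 6 and 64–91 to Week 12. The section says that this algorithm "ensures that all observations collected at an ET visit or any other unscheduled visit will be mapped to an analysis visit". For several scores in one window the rule is: "If more than one observation falls within a particular trial day interval, then the last observation within that interval is used". All values stay in the listings, but "only the last observation will be used for the by-visit analysis or summary". The one timing exclusion is in the table footnote: "Evaluations occurring more than seven days after the last dosing date of IMP in the open-label treatment period will be excluded from the efficacy analyses". In its body text, SAP 10.1 states the same 7-day limit without confining it to efficacy.

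**Schedule.** Protocol 3.6.4.5.5: "The MMSE is completed at baseline and Week 12 or ET". Protocol 3.6.4.5.4, on the follow-up form: "Sheehan-STS form will be completed baseline and Week 12/ET during Trial 331-201-00182". Protocol Table 3.6-1 agrees on both, and places SAS, AIMS and BARS at baseline, Week 6 and Week 12/ET. Protocol 3.7.3.2 requires subjects withdrawn before Week 12 to have the Week 12/ET assessments when they withdraw.

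**Summaries.** SAP 9.6 on MMSE: "Descriptive statistics will be summarized at each visit using the OC data set", with LOCF at the last visit. SAP 9.5 and 9.7 do the same for SAS/AIMS/BARS and Sheehan-STS.

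**The concern.** A subject who leaves early produces a full set of scale scores on whatever day the ET visit falls, and SAP 10.1 gives those scores the label of the nearest window. Nothing limits the by-visit rows to visits where the scale is due, and a scheduled score has no priority over an ET score.

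Two things follow. Some rows would exist only because someone left or had an unscheduled assessment. In the Week 6 SAS/AIMS/BARS row, a score taken at the Week 6 visit can be dropped in favour of a later exit score. Both sit badly with SAP 5.2, which defines observed cases as what was actually recorded at each visit.

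Long-term safety and tolerability is the only stated objective, and these scales carry its cognition, suicidality and extrapyramidal data. A mean-change table running from Week 1 to Week 12 would read as a time course although the subjects behind each row differ. The summaries are descriptive, so no model adjusts for the change in who is counted.

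**Working it through.** The plan gives no figure to reproduce: the sample size is not power-based and no early-termination rate is stated. The check is day arithmetic on SAP Table 10.1-1 against Protocol Table 3.6-1.

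**Step 1: windows against schedule** (length = last day − first day + 1)

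| Window | Days | Length | Target | MMSE, Sheehan-STS due (protocol)? | SAS/AIMS/BARS due? |
|---|---|---|---|---|---|
| Week 1 | 2–10 | 9 | 7 | no | no |
| Week 2 | 11–28 | 18 | 14 | no | no |
| Week 6 | 29–63 | 35 | 42 | no | yes |
| Week 12 | 64–91 | 28 | 84 | yes | yes |

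The windows have no gaps or overlaps. ET days that fall in a window with nothing scheduled:
- MMSE and Sheehan-STS: 9 + 18 + 35 = 62 days (Days 2–63).
- SAS/AIMS/BARS: 9 + 18 = 27 days (Days 2–28).

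Those rows can contain only ET or unscheduled scores.

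**Step 2: replacement at Week 6.** If the scheduled visit is on Day v, an ET score replaces it on 63 − v later days. With the ±2-day tolerance, v runs from 40 to 44:
- v = 40: 23 days
- v = 42: 21 days
- v = 44: 19 days

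An ET on Days 29–39 (11 days) comes before any on-time Week 6 visit and enters the row with no scheduled score.

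**Step 3: illustration of size.** None of these assumptions comes from the documents: N entrants; a proportion e terminating early; ET day uniform over Days 2–81 (80 days); ET visit within 7 days of last dose; Week 6 visit on Day 42; no unscheduled scores.

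For N = 150 and e = 10%, exits per day = 15/80 = 0.1875.
- MMSE and Sheehan-STS rows, all ET scores: Week 1, 9 × 0.1875 = 1.7; Week 2, 18 × 0.1875 = 3.4; Week 6, 35 × 0.1875 = 6.6.
- Week 6 SAS/AIMS/BARS, replaced (Days 43–63): 21 × 0.1875 = 3.9.
- Week 6 SAS/AIMS/BARS, ET score only (Days 29–42): 14 × 0.1875 = 2.6.
- Subjects with a scheduled Week 6 score: 150 − 15 + 39 × 0.1875 = 142.3.
- Row size: 142.3 + 2.6 = 144.9. ET share: 6.6/144.9 = 4.5%.

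N cancels from the share. Only exits on Days 2–28 are absent from the row, so share = (35e/80)/(1 − 27e/80). The replaced part has 21 in place of 35, and the ET-only part has 14.

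| e | ET share of row | Replaced | ET only |
|---|---|---|---|
| 5% | 2.2% | 1.3% | 0.9% |
| 10% | 4.5% | 2.7% | 1.8% |
| 20% | 9.4% | 5.6% | 3.8% |

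If ET scores differed from the others by 1 SD, the Week 6 mean would move by share × 1 SD, about 0.02 to 0.09 SD.

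**Step 4: route to the last visit.** SAP 5.2 builds LOCF from data recorded at a scheduled visit or carried forward from one, and does not carry baseline forward. The mapping in SAP 10.1 is what gives an ET score a visit. If it were removed and nothing else changed, an early leaver whose only post-baseline MMSE is at ET might have no last-visit value.

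**The case against.** The case for leaving the text alone has several parts.

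- **Reading of SAP 9.5–9.7.** A summary at each visit can be taken to mean each visit where the scale is collected, so the odd rows might never be printed. That is possible, but SAP 10.1 names MMSE and Sheehan-STS as covered by the windows and maps their ET scores to visits. The ambiguity stands and is itself worth removing.
- **Last-in-window is a legitimate safety convention.** It keeps on-treatment exit scores in view. This stands as a matter of choice, but it does not justify rows with no scheduled score.
- **Nothing is hidden.** Listings keep every value beside the CRF visit, and the derived week is footnoted. The scheduled Week 6 score is lost from the summary only.
- **Small effect.** The summaries are descriptive, and sparse rows would be visible wherever n is shown. This stands.

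A reader might also infer more than the documents support:

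- **That the off-schedule rows consist only of dropouts.** Unscheduled scores from continuing subjects are mapped too.
- **That exit scores make the rows look worse.** Subjects can leave for adverse events or intolerance, but also by request, for noncompliance or for COVID-19 reasons. The direction is unknown.
- **That every scale is overwritten.** Replacement can be shown only for SAS/AIMS/BARS at Week 6. The CMAI and CGI-S visit schedule is not visible in the public text.
- **That the Sheehan-STS finding is certain.** SAP 10.2.6 has the follow-up form completed at every visit after screening, contrary to the protocol. If that governed, the issue at Weeks 1, 2 and 6 would be replacement.
- **That ET mapping can be dropped at no cost.** Step 4 of the working shows why SAP 5.2 must change as well.

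**Conclusion.** The point holds within limits. On the text as written, the by-visit rows for MMSE at Weeks 1, 2 and 6, for SAS/AIMS/BARS at Weeks 1 and 2, and (on the protocol schedule) for Sheehan-STS at Weeks 1, 2 and 6 would contain no scheduled scores. This follows from the day windows alone and needs no assumption about dropout. The Week 6 replacement also follows from the text, for ET visits within the 7-day limit.

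The size does rest on assumptions. The 5–20% early termination, uniform exit timing and 1-SD difference are illustrative. On those figures the Week 6 SAS/AIMS/BARS effect is small, and the off-schedule rows are the more misleading part. The primary analysis of adverse events does not use these windows, and there is no formal comparison to distort. This is a worthwhile clarification and does not threaten the trial's main conclusion.

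**What to change.** - **SAP 10.1 and 9.5–9.7:** show by-visit observed-case rows only for visits where the scale is scheduled in Protocol Table 3.6-1. When a scheduled score shares a window with an ET or unscheduled score, use the scheduled one in the summary. Keep all values in the listings.
- **SAP 5.2:** state that eligible ET scores feed the last-visit (Week 12/ET) LOCF summary, so that no ET data are lost.
- **SAP 10.2.6:** reconcile the Sheehan-STS visits with Protocol 3.6.4.5.4 and Table 3.6-1.
- **SAP 10.1, 7-day limit:** make the body text and the table footnote agree on whether it covers safety scales.

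The cost is minor rewording and a windowing flag in the programs. ET scores would no longer appear in by-visit rows where the scale is not scheduled or where a scheduled score exists. An ET score on Days 29–63 from a subject with no Week 6 visit would stay in the Week 6 SAS/AIMS/BARS row. In the illustration that leaves 0.9–3.8% of the row as ET scores, down from 2.2–9.4%.

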10.2 Scales: Rules for Scoring and Handling of Missing Data

10.2.1 Cohen-Mansfield Agitation Inventory

The CMAI consists of 29 items all rated on a 1 to 7 scale with 1 being the “best” rating and 7 being the “worst” rating. The CMAI total score is the sum of ratings for all 29 items. The possible total scores are from 29 to 203. The CMAI total score will be unevaluable if less than 24 of the 29 items are recorded. If 24 to 28 of the 29 items are recorded, the total score will be the mean of the recorded items multiplied by 29 and then rounded to the first decimal place.

Factor 1: Aggressive behavior: Hitting (including self), kicking, scratching, grabbing onto people, pushing, hurt self or other (cigarette, hot water, etc.), throwing things, cursing or verbal aggression, spitting (include at meals), tearing things or destroying property, screaming, biting.

Criteria for agitated status based on Factor 1:

- at least one aggressive behavior occurring at a frequency of at least 4; or
- at least two aggressive behaviors occurring at a frequency of at least 3; or
- at least three aggressive behaviors occurring at a frequency of at least 2;

SAP 331-201-00182

Factor 2: Physically nonaggressive behavior: Pace, aimless wandering, trying to get to a different place, general restlessness, inappropriate dress or disrobing, handling things inappropriately, performing repetitious mannerisms.

Criteria for agitated status based on Factor 2:

- at least one physically nonaggressive behavior occurring at a frequency of at least 5; or
- at least two physically nonaggressive behavior occurring at a frequency of at least 4; or
- at least three physically nonaggressive behavior occurring at a frequency of at least 3; or
- at least four physically nonaggressive behavior occurring at a frequency of at least 2;

Factor 3: Verbally agitated behavior: Complaining, constant unwarranted request for attention or help, repetitious sentences or questions, negativism.

Criteria for agitated status based on Factor 3:

- at least one verbally agitated behavior occurring at a frequency of at least 5; or
- at least two verbally agitated behavior occurring at a frequency of at least 4; or
- at least three verbally agitated behavior occurring at a frequency of at least 3; or
- at least four verbally agitated behavior occurring at a frequency of at least 2;

Factor 4: Hiding things, hoarding things.

The following items are not included in factors derivation¹: Intentional Falling; Making Verbal Sexual Advances; Making Physical Sexual Advances; Strange Noises (weird laughter or crying); Eating or Drinking Inappropriate Substances.

10.2.2 Clinical Global Impression-Severity of Illness Scale

The severity of agitation for each subject will be rated using the Clinical Global Impression-Severity of Illness Scale (CGI-S). To perform this assessment, the investigator (or designee) will answer the following question: "Considering your total clinical experience with this particular population, how mentally ill (as related to agitation) is the subject at this time?" Response choices are 0 = not assessed; 1 = normal, not at all ill; 2 = borderline mentally ill; 3 = mildly ill; 4 = moderately ill; 5 = markedly ill; 6 = severely ill; and 7 = among the most extremely ill subjects. The score 0 (not assessed) will be set to missing. The CGI-S is therefore a 7-point scale from 1 through 7.

SAP 331-201-00182

10.2.3 Simpson-Angus Scale

The Simpson-Angus Scale is a rating scale used to measure EPS. The Simpson-Angus Scale is a 10-item scale, with each item rated from 0 to 4, with 0 being normal and 4 being the worst. The Simpson-Angus Scale total score is the sum of ratings for all 10 items, with possible total scores from 0 to 40. The Simpson-Angus Scale total score will be un-evaluable if less than 8 of the 10 items are recorded. If 8 or 9 of the 10 items are recorded, the total score will be the mean of the recorded items multiplied by 10 and then rounded to the first decimal place.

10.2.4 Abnormal Involuntary Movement Scale

The AIMS is a 12-item scale. The first 10 items are rated from 0 to 4 (0 = best, 4 = worst). An item score of 0, depending on the item, either means: no abnormal involuntary movement (AIM), or no incapacitation due to AIM, or no awareness of AIM. An item score of 4 either means: severe AIM, or severe incapacitation due to AIM, or being aware of, and severe distress caused by AIM. Items 11 and 12, related to dental status, have dichotomous responses, 0 = no and 1 = yes. The AIMS total score is the sum of the ratings for the first seven items. The possible total scores are from 0 to 28. The AIMS total score will be un-evaluable if less than 6 of the first 7 items are recorded. If 6 of the items are recorded, then the total score will be the mean of the recorded items multiplied by 7 and then rounded to the first decimal place.

10.2.5 Barnes Akathisia Rating Scale

Barnes Akathisia Rating Scale (BARS) will be used to assess the presence and severity of akathisia. This scale consists of 4 items. Only the 4th item, the Global Clinical Assessment of Akathisia, will be evaluated in this trial. This item is rated on a 6-point scale, with 0 being best (absent) and 5 being worst (severe akathisia).

10.2.6 Sheehan Suicidality Tracking Scale

Suicidality will be monitored during the trial using the Sheehan-STS. The Sheehan-STS is a prospective scale that assesses treatment-emergent suicidal thoughts and behaviors. Each item of the Sheehan-STS is scored on a 5-point Likert scale (0 = not at all; 1 = a little; 2 = moderate; 3 = very; and 4 = extremely). The Sheehan-STS can be analyzed as individual item scores, suicidal ideation subscale score, suicidal behavior subscale score, or total score. The trial will use the “Screening” and “Since Last Visit” version of the scale. The “Screening” Sheehan-STS form will be completed at the screening visit to determine eligibility. Any subject with evidence of serious risk of suicide based on the Sheehan-STS, ie,

SAP 331-201-00182

a score of 3 or 4 on any one question 2 through 6 or 11 or a score of 2 or higher on any one questions 1a, 7 through 10, or 12, or who, in the opinion of the investigator, present a serious risk of suicide should be excluded from the trial. The “Since Last Visit” Sheehan-STS form will be completed at all other visits. The medical monitor should be contacted if a score of 3 or 4 on any one question 3 through 6 or 11 or a score of 2 or higher on any one questions 1a, 7 through 10, or 12, or 18, or if suicide results in death.

10.2.7 Mini-Mental State Examination

The MMSE is a brief practical test for assessing cognitive dysfunction. The test consists of 5 sections (orientation, registration, attention and calculation, recall, and language) and has a total possible score of 30. The MMSE is used for screening subjects and is also to be completed at Week 12/ET.

The MMSE is a 19-item scale. Items 1 to 10, 15, and 17 to 19 are rated on a scale from 0 to 1, item 14 is rated on a 0 to 2 scale, items 11, 13 and 16 are rated on a scale from 0 to 3, and Item 12 is rated on a scale from 0 to 5. Low scores are the worst, high scores are the best. The MMSE total score is calculated by adding the individual item scores. The possible range for the MMSE total score is from 0 to 30. If the maximum total of the missing items could contribute more than 6 points to the total score then the total score will be set to missing. Otherwise, a mean non-missing items score will be calculated by summing the non-missing items and dividing them by the maximum score possible from the non-missing items. For missing items with possible scores from 0 to 1, the mean score will be imputed for each missing item. If item 14 is missing, two times this mean will be imputed for item 14. If items 11, 13, or 16 are missing three times this mean for will be imputed each missing item. If item 12 is missing 5 times then this mean will be imputed for item 12. After all by-item imputation has been done, the individual item scores will be added and this sum will be rounded to the first decimal place to arrive at an imputed total score. In other terms, the MMSE total score is simply the mean non-missing items score multiplied by 30, and then rounded to the first decimal place.

SAP 331-201-00182

11 References

¹ Rabinowitz J, Davidson M, Paul De Deyn P, Katz I, Brodaty H, Cohen-Mansfield J. Factor Analysis of the Cohen-Mansfield Agitation Inventory in Three Large Samples of Nursing Home Patients With Dementia and Behavioral Disturbance. *Am J Geriatr Psychiatry*. 2005;13(11):991-8.

Until the information herein is released by Otsuka to the public domain, the contents of this document are Otsuka confidential information and should not be duplicated or re-distributed without prior written consent of Otsuka.

